8.4.4 Storage

Study drug should be stored by the study site at controlled room temperature, Store at 15° to 30°C (59° to 86°F). If the temperature of study drug storage in the clinic/pharmacy exceeds or falls below this range, this will be reported to the research program manager and PI and captured as a deviation. Subjects will be instructed to store the medication in the MEMS cap containers at room temperature according to the instructions outlined on the Drug Administration Instructions.

8.5 Study Drug Accountability

An accurate and current accounting of the acquisition, dispensing, return, and destruction of study drug for each participant will be maintained in an investigational drug accountability log by study staff throughout the course of the study.

8.6 Measures of Treatment Compliance

Study medications will be dispensed by the study clinician in MEMS cap dispensers with dosing instructions, date of dispensing, prescribing clinician, a 24-hour telephone study phone number for medical emergencies, and advisements against drug combinations. Each dispenser opening is recorded as a medication event in a remote database in real time. MEMS cap dispensers have been shown to be reliable for real time monitoring of medication adherence, even in resource-limited settings.¹¹⁷ We have had great success with electronic medical monitoring devices in prior studies among MSM.^{53, 84} The Subjects will be asked to bring in their study drug at in-office visits. The Subjects will be asked to document any adverse events that occur during the week.

9. STUDY PROCEDURES AND GUIDELINES

A Schedule of Events representing the required testing procedures to be performed for the duration of the study. Prior to conducting any study-related activities, written informed consent and the Health Insurance Portability and Accountability Act (HIPAA) authorization must be signed and dated by the subject or subject's legal representative. If appropriate, assent must also be obtained prior to conducting any study-related activities.

9.1 Clinical Assessments

9.1.1 Concomitant Medications

All concomitant medication and concurrent therapies will be documented at Baseline/Screening and at Month 1, Month 2 and Month 3 safety lab visits. Dose, route, unit frequency of administration, and indication for administration and dates of medication will be captured.

9.1.2 Demographics

Demographic information (date of birth, gender, race) will be recorded at Screening.

9.1.3 Medical History

Relevant medical history, including history of current disease, other pertinent respiratory history, and information regarding underlying diseases will be recorded at Screening.

9.1.4 Physical Examination

A complete physical examination will be performed by the clinician at Enrollment, Month 1, Month 2 and Month 3 visits. Qualified staff (MD, NP, RN, and PA) may complete the abbreviated physical exam at all other visits. New abnormal physical exam findings must be documented and will be followed by a physician or other qualified staff at the next scheduled visit.

9.1.5 Vital Signs

Body temperature, blood pressure, pulse and weight will be performed after resting for 5 minutes on Screening, Enrollment and Month 1, Month 2 and Month 3 visits.

9.1.6 Safety Lab Assessment

Safety lab assessments will take place at screening, months 1, 2, and 3 visits. Blood specimens will be collected for monthly safety lab assessments via venipuncture by clinicians or research associates with certified phlebotomy training. Medications taken 30 days prior to enrollment and while enrolled in the study will be documented on a concomitant medications form.

9.1.7 HIV risk reduction counseling and testing

All participants will receive standard HIV risk reduction counseling at enrollment and month 3 with HIV rapid antibody test and pooled viral load (HIV-negative participants) and CD4 testing (HIV-positive participants).¹⁰⁴ Participants with positive rapid tests will be given a confirmatory Western Blot assay and will receive HIV-counseling and referrals to HIV service providers. Participants newly diagnosed with HIV at screen will be referred to community resources and will be contacted for rescreening in the subsequent month.

9.2 Other Clinical Procedures

9.2.1 Medical Management (MM) counseling for alcohol use:

This study's aim is to determine efficacy of a pharmacologic intervention to reduce binge drinking, against a background of relatively brief counseling that would be feasible in a clinical setting with limited resources. Thus, we will adapt a manualized version of the MM brief counseling platform used in NIAAA's COMBINE study.^{72, 105} In that trial, naltrexone with MM showed the most significant reductions in heavy drinking days (Hazard Ratio: 0.72; p=0.02) compared to 7 other treatment conditions.⁷² MM has been used in a targeted pharmacotherapy trial⁸¹ and our team has successfully used MM in alcohol pharmacologic trials. MM is a low-intensity supportive program designed to increase problem recognition and enhance motivation to change maladaptive alcohol use patterns. Participants will receive individual 20 minute MM sessions weekly from trained staff supervised by a clinical psychologist, with monthly quality assurance sessions.

9.2.2 Behavioral survey measurements:

Standardized and validated behavioral measures^{106-109, 111, 112, 115} will be assessed using audio computer administered surveys (ACASI) to minimize underreporting of risk activities and standardize data collection.^{106, 107} To minimize potential social desirability bias, staff will not have access to data during the trial.

9.2.3 Measures of adherence:

The study will collect self-reported adherence via weekly modified TLFB assessments, similar to prior targeted naltrexone studies^{11, 81} and via daily SMS text messages. Pill counts at weekly visits will also assess adherence. **MEMs cap dispensers** will be used to track medication adherence daily; each dispenser opening is recorded as a medication event in a remote database in real time. MEMs cap dispensers have been shown to be reliable for real time monitoring of medication adherence, even in resource-limited settings.¹¹⁷ We have had great success with electronic medical monitoring devices in prior studies among MSM.^{53, 84}

9.2.4 Ecological Momentary Assessments:

As with our Project iN pilot study, participants will receive daily SMS texts to collect data on alcohol consumption, number of drinks on drinking days, and targeted medication administration prior to anticipated drinking sessions. Messages will use short-hand notations to maintain participant confidentiality. Participants will be trained on text-messaging procedures and receive a reference guide during enrollment (see sample from Project iN study in the appendix). Participants will be encouraged to regularly delete text messages and encrypt their phone with passwords for privacy.

9.2.5 Adverse Events

Potential AEs will be monitored using a checklist of most common AEs associated with naltrexone similar to prior Phase IV naltrexone studies¹¹ and will follow the "Division of AIDS Table for Grading the Severity of Adult and Pediatric Adverse Events" and UCSF IRB reporting guidelines.¹¹⁶ Safety monitoring will include the assessment, follow-up, and reporting of clinical/serious AEs (start and stop dates and times), severity/grade, outcome, treatment and relation to study drug will be recorded on the case report forms as well as in the electronic database.

9.3 Clinical Laboratory Measurements

9.3.1 Hematology

Blood will be obtained and sent to San Francisco General Hospital laboratory for a complete blood count (hemoglobin, hematocrit, red blood cell count, white blood cell count, white blood cell differential, and platelet count).

9.3.2 Blood Chemistry Profile

Blood will be obtained and sent to San Francisco General Hospital Laboratory for determination of (list as applicable) serum sodium, potassium, chloride, bicarbonate, random glucose, BUN, creatinine, aspartate aminotransferase (AST/SGOT), alanine aminotransferase (ALT/SGPT), alkaline phosphatase, total bilirubin, direct bilirubin, gamma-glutamyl transferase (GGT), albumin and LDH.

9.3.4 Pregnancy Test

A urine pregnancy test will be obtained from female subjects who are of childbearing age prior to their participation in the study and during the safety lab visits at month 1, month 2 and month 3 visits.

9.3.5 Urinalysis

9.3.5.1 Urinalysis for other classes of substance use: Urine samples will be collected weekly and tested for methamphetamine, cocaine, opioids, and other substances of abuse using MEDTOX EZ-SCREEN cups. Positive results will be confirmed by further urine testing through the laboratory at San Francisco General Hospital.

9.3.5.2 Urinalysis for novel alcohol biochemical markers: Urine samples will be collected at enrollment and monthly and tested for ethyl glucuronide (EtG) to determine recent alcohol consumption. EtG is a relatively novel, highly sensitive indicator for recent alcohol consumption; this alcohol biomarker is detectable in urine for approximately 72 hours).¹¹⁸⁻¹²¹ The PI has used EtG to evaluate the efficacy of another pharmacologic intervention in reducing alcohol consumption in a trial funded by the Department of Defense¹²² with [name], a consultant in the proposed study. Urine samples will be tested via liquid chromatography-mass spectrometry through the Redwood Toxicology Laboratory, Inc., the same lab used by [name] ongoing pharmacologic trials on alcohol dependence at the San Francisco Veteran's Affairs Medical Center. EtG quantitative results will be dichotomized using established cutoff values recommended by the Substance Abuse and Mental Health Services Administration (SAMHSA) to distinguish between positive and negative specimens.^{119, 121} Whenever possible we will schedule participants for their weekly visits on Mondays and Tuesdays, given that binge drinking is likely to be higher over the weekend compared to the remainder of the week.

9.3.6 Dried Blood Spot (DSB) Testing for Phosphatidylethanol:

Phosphatidylethanol (PEth)—a phospholipid formed only in the presence of alcohol—is a novel, *direct* biochemical marker of alcohol that has shown high (>95%) sensitivity and specificity to detect heavy drinking over a period of 2-3 weeks in several studies of dependent patients and abstainers. In persons with HIV, recent validation studies found that PEth, using a cutoff of >8 ng/mL, was 88% sensitive and 89% specific for alcohol consumption in the prior 21 days (3 weeks), and 95% sensitive and 73% specific for heavy alcohol consumption (i.e., exceeding the NIAAA cutoffs). DSB samples will be collected at enrollment, weeks 3, 6, 9, 12, and post-

treatment visits at month 1, 3, and 6. Staff will use sterile lancets for fingersticks (or we will aliquot blood from a venipuncture specimen tube) to collect drops of blood (less than 5ml) to apply onto Whatman 903 filter paper (Whatman, Maidstone, UK). Samples will be dried overnight inside a drying box using standardized methods. PEth testing of DBS samples will be conducted at the United States Drug Testing Laboratories in Des Plaines, IL, one of the few laboratories that conduct this test worldwide. The testing will be conducted using an Agilent 6460 liquid chromatography-tandem mass spectrometry (LC-MS/MS) system following extraction into methanol, as previously published.

9.3.7 Genetic and Biomarker Testing: Blood samples will be stored at the University of California San Francisco, School of Nursing Genomics Lab for future genetic, epigenetic and micro RNAstudies, as well as other studies that elucidate the biologic processes by which alcohol use may contribute to morbidity and mortality. Research studies will be restricted to health conditions associated with alcohol use. These may include testing to determine the presence of the A118G SNP and other mutations relevant to the moderation of naltrexone's effects on the μ -opioid receptor gene (OPRM1). Additionally, we may test for the expression of biomarkers associated with innate immune activation (i.e., sCD14, neopterin, and tryptophan/kynurene ratio) and inflammation (i.e., IL-6, TNF- R1).

10 EVALUATIONS BY VISIT

10.1 VISIT 1 (SCREENING VISIT—WEEK 1)

Review the study with the subject (subject's legal representative) and obtain written informed consent and HIPAA authorization and assent, if appropriate.

Assign the subject a unique screening number.

Record demographics data.

Record medical history, including a history of mental health, sexual behaviors and substance use, diagnosis date, and prior Alcohol treatments.

Record concomitant medications.

Perform a complete physical examination.

Collect urine sample for alcohol, opiates, and other substances test. If capable of becoming pregnant then a pregnancy test. Record results.

10.2 Visit 2 (Screening Visit – week 2)

Perform and record vital signs.

Perform and record results of blood pressure testing.

Collect blood for clinical laboratory tests (chemistry, hematology, HIV test, pooled viral load test. If HIV positive, a CD4 test).

Collect blood for Genetic and Biomarker Testing if you agreed to participate in a genetic and biomarker sub-study that will involve storage of blood samples to be used for testing. Testing will be confined for genes and biomarkers of health conditions related to alcohol use.

Collect and record contact information

10.3 Visit 3 (Enrollment Visit – month 1)

Assign randomization. You are assigned by a computer by chance to either thnaltrexone or placebo groups.

Collect urine to test for alcohol, opiates, and other substances.

If capable of becoming pregnant, we will collect urine and perform a pregnancy test. Provide study medication (naltrexone or placebo) in medical monitoring devices (“MEMS” containers). MEMS devices will record each time you open the container to retrieve a study medication capsule. Provided with a Wallet Card that explains that you may or may not be on a study medication (naltrexone or placebo). This card will provide the study clinician’s pager number who can provide information to other doctors in the event of an emergency. The card will also instruct the emergency room or other doctor providing treatment to provide information to the study clinician about the care they provide.

Collect blood sample to test for alcohol (PEth test).

Perform ACASI questionnaire on a computer.

Meet with counselor about alcohol consumption

Initiate Ecological Momentary Assessments

10.4 Visit 4 (weeks 1, 2, 3, 5, 6, 7, 9, 10, and 11))

Record any Adverse Experiences and dosing compliance by downloading MEMs cap dispenser.

Meet with the counselor regarding alcohol consumption and use of the study medication.

Collect urine sample to test for alcohol, opiates and other substances. If capable of becoming pregnant, we will also conduct a pregnancy test.

Answer ACASI questions on a computer

Receive the study medication: if needed, you will be given more of the study medication (except at the week 12 visit).

Meet with the study doctor or nurse: to talk about any problems with the study medication or any changes in your health or medications if needed. A physical exam may be done.

Collect a blood sample (weeks 3, 6, & 9): to test for alcohol. A few drops of blood will be collected by a lancet stick to your finger or a venipuncture blood draw.

10.5 Visit 5 (Month 1, 2 and 3 with visit window 2 weeks before visit and 2 weeks after visit)

All the same procedures as the weekly visits **PLUS** these additional procedures:

Answer ACASI questions on a computer about your mood, your recent sexual behavior and drug use, and your feelings about being in the study.

Record any Adverse Experiences and dosing compliance.

Record changes to concomitant medications.

Meet with the study doctor or nurse: to talk about any problems with the study medication or any changes in your health or medications if needed. A physical exam may be done.

Collect blood for clinical laboratory tests (chemistry, hematology). At month 3 visit, collect blood for HIV test, pooled viral load test. If HIV positive, a CD4 test.

Collect a blood sample: to test for alcohol. A few drops of blood will be collected by a lancet stick to your finger or a venipuncture blood draw.

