A review of the literature concluded that in patients treated for heroin or alcohol dependence, naltrexone does not cause clinically significant liver disease or exacerbate pre-existing liver disease.⁷¹ However, naltrexone has the capacity to cause hepatocellular injury in excessive doses and is contraindicated in acute hepatitis and liver failure.⁶⁹ Patients with these conditions will be excluded from our trial. Naltrexone is also contraindicated in patients who are currently dependent on opioids or in acute opioid withdrawal. The team anticipates that few participants will be excluded by virtue of current opioid use; for example, in our recently published mirtazapine study, only 7% of MSM met criteria for opioid dependence. Although the opioid blockade produced by naltrexone is surmountable, this situation requires careful medical management by trained personnel in settings equipped for resuscitation. Attempts by patients to overcome naltrexone's opioid antagonism may lead to an overdose. Naltrexone may also precipitate severe opiate withdrawal, including mental status change, nausea, vomiting, diarrhea, and dehydration in patients who are not opioid-free for a minimum of 7 to 10 days.⁶⁹ For this reason, urine opioid testing is needed to screen all potential participants for opioid use. Patients who have a foreseeable need for opioid pain management (e.g. potential elective surgery in the study period) will also be excluded. Additionally, all patients will be fully informed verbally and in the written consent form about the potential for overdose by attempting to overcome naltrexone's opioid antagonism.

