6.3 Exclusion Criteria

- (1) Any psychiatric (e.g. depression with suicidal ideation) or medical condition that would preclude safe participation in the study;
- (2) known allergy/previous adverse reaction to naltrexone;
- (3) current use of/ dependence on any opioids or a known medical condition which currently requires/may likely require opioid analgesics;
- (4) opioid-positive urine at enrollment;
- (5) current CD4 count < 200 cells/mm³;

- (6) moderate/severe liver disease (AST, ALT \geq 3 times upper limit of normal);
- (7) impaired renal function (creatinine clearance $<$ 50 ml/min);
- (8) currently participating in another intervention research study with potential overlap;
- (9) alcohol dependence as determined by SCID criteria (participants with non-dependent alcohol use disorders/symptoms of alcohol abuse [per DSM-IV] are *eligible*)
- (10) any condition that, in the principal investigator and/or study clinician's judgment interferes with safe study participation or adherence to study procedures;
- (11) not having a cell-phone that can send and receive text messages;

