APPENDIX 1. STUDY PROCEDURES

TABLE 2. Study Procedures

	Visit Type				
	SCR	BL	Wk	Mos. 1 & 2	Mos. 3
Informed consent	X				
Safety lab assessment	X			X	X
Rapid HIV test* or CD4	X				X
HIV risk reduction counseling	X				X
Complete medical history, physical exam & SCID	X				
Vital signs, weight	X	X		X	X
Symptom driven physical exam		X			X
Targeted Medication Training	X				
Text messaging (SMS)			X		
Training			X		
Randomization			X		
Urine testing for opiates	X	X			
Urine testing for ethyl glucuronide (ETG)	X	X	X	X	X
Audio Computer Assisted Survey Instrument (ACASI)		X	X	X	X
Adverse event assessment			X	X	X
Alcohol Use Medical Management Counseling		X	X		

a ±2

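### Section 10.3 lists randomisation ahead of the enrollment opiate urine that decides eligibility, and nothing requires the result before allocation or dispensing

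*Combined protocol and SAP*

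**What the plan says.** Section 10.3 lists the steps of the enrollment visit. The first is "Assign randomization. You are assigned by a computer by chance", the second is "Collect urine to test for alcohol, opiates, and other substances", and the provision of study medication comes after both.

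Exclusion 4 in Section 6.3 is "opioid-positive urine at enrollment". Section 8.1 describes the men who are randomly assigned as eligible. Section 2.1 gives the purpose of the test: "urine opioid testing is needed to screen all potential participants for opioid use".

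There is also an earlier urine. Section 10.1 (Visit 1, screening week 1) has "Collect urine sample for alcohol, opiates, and other substances test", and the row "Urine testing for opiates" in Appendix 1 is marked at both screening and baseline. Section 9.3.5.1 says that urines are "tested for methamphetamine, cocaine, opioids, and other substances of abuse using MEDTOX EZ-SCREEN cups" and adds: "Positive results will be confirmed by further urine testing through the laboratory at San Francisco General Hospital".

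Four further rules decide what happens to an ineligible man once randomised:
- Section 13 classes failure of the entry criteria as a protocol violation and leaves withdrawal to the principal investigator.
- Section 4.1 analyses outcomes by random assignment, whether or not drug was taken.
- Section 12.3 does not replace men who withdraw from study treatment.
- Section 15.1 limits the safety population to eligible, randomised men who took study drug.

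**The concern.** A test that can exclude a man should be read before he is allocated. If staff work down Section 10.3 as printed, allocation comes first and the protocol never tells them to wait for the result. An excluded man could then enter the trial and, because no hold on dispensing is written, could also receive study drug.

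Three things are at stake. The first is the integrity of eligibility: each such man is an avoidable protocol violation, and whether he continues is an individual decision taken after allocation. The second is safety: Section 2.1 warns that naltrexone may precipitate severe opiate withdrawal in patients who have not been opioid-free for at least 7 to 10 days. The third is reporting: if he is dosed, the word *eligible* in Section 15.1 could remove him from the safety analysis, although his safety data would matter most.

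**Working it through.** **Order of procedures.** This part is settled by setting the sections side by side.

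1. Sections 6.3, 2.1 and 8.1 together make the enrollment opiate urine an eligibility gate.
2. Section 10.3, the step list for that visit, places allocation ahead of the urine and dispensing after it. It contains no instruction to read the result before either.
3. Section 4.1 says only that randomisation takes place upon enrollment. Appendix 1 shows that the urine is taken at baseline, but its layout did not survive text extraction, so the position of its randomisation row is not relied on here.
4. The Visit 1 urine narrows the gap without closing it. The synopsis allows up to 30 days of screening, so that urine can be older than the 7 to 10 opioid-free days in Section 2.1. The men at issue are those who turned positive after Visit 1 or were missed there.
5. Section 9.3.5.1 sends positive results to a laboratory. It does not say whether randomisation waits, and its text concerns weekly urines, so applying it to the enrollment urine is an inference.

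**Scale.** The plan's power statement (Sections 15.3 and 15.6) is 80% power, two-sided 5%, for a 27% reduction in binge occasions, with 120 enrolled and 90% retained. That leaves 0.90 × 120 = 108 men, or 54 per arm. The figure cannot be reproduced independently, because the control mean, over-dispersion and within-subject correlation are taken from an earlier trial and not stated. It can only be inverted:

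- SE of the log rate ratio = |ln 0.73| / (1.960 + 0.842) = 0.3147 / 2.802 = 0.1123. By construction this returns 80%.

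Let q be the share of randomised men who are ineligible. No rate is given, so q is assumed.

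- Kept in the analysis untreated: rate ratio = 1 − 0.27(1 − q); power = Φ(|ln RR| / 0.1123 − 1.960).
- Dropped from the analysis: 54(1 − q) per arm; power = Φ(2.802 × √(1 − q) − 1.960).

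| q (assumed) | Men of 120 | RR if kept | Power, kept untreated | Power, dropped |
|---|---|---|---|---|
| 0 | 0 | 0.730 | 80.0% | 80.0% |
| 1% | 1.2 | 0.733 | 79.1% | 79.6% |
| 2% | 2.4 | 0.735 | 78.1% | 79.2% |

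The loss at 1–2% is 0.9 to 1.9 points if the men are kept untreated and 0.4 to 0.8 points if they are dropped.

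**The case against.** The strongest reply is that Section 10.3 is a checklist and not a timetable. It is never labelled chronological, and it uses consent-form language. Read as a clock, it would also place the enrollment PEth sample and the ACASI after dispensing, and Section 10.4 would have men receive drug before seeing the clinician. Sections 2.1, 6.3 and 8.1 show that the intent is to randomise eligible men only. Section 8.4 adds that kits arrive already randomised, so allocation may take practical effect only at dispensing, which is listed after the urine.

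Much of this stands: the documents do not prove that allocation precedes the test in practice. It does not remove the point. Section 10.1 opens with consent, which Section 9 requires before any study activity, so staff could reasonably follow these lists in order. If no order is meant, the protocol states none for an eligibility test and an allocation at the same visit. Even if allocation takes effect at dispensing, collecting a urine is not the same as having its result.

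A reader might go further and infer that opioid-positive men must then be dropped or left untreated, and that intention-to-treat is broken. The documents say neither. Section 13 leaves withdrawal to the principal investigator, Section 12.1 encourages men who stop treatment to complete their visits, and Section 4.1 keeps them in the analysis as randomised.

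A reader might also take the 7% in Section 2.1 as the rate, giving 8.4 men and 73.0% power if kept untreated (77.1% if dropped). That figure is opioid dependence in an earlier mirtazapine trial. It is not the rate of positive enrollment urines here, after exclusion 3 and a screening urine have already removed men.

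**Conclusion.** The point holds as a gap in the written sequence. The protocol makes the enrollment opiate urine an entry criterion, lists allocation ahead of it, and never requires the result before allocation or dispensing. On the listed order, an excluded man could be randomised and possibly dosed, stay in the intention-to-treat analysis, and be left out of the safety population.

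The number of such men is not given and is probably small. The power loss of at most about two points rests on an assumed 1–2% share, equal in both arms, on a standard error back-solved from the plan's own claim, and, in the kept case, on untreated men drinking at the placebo rate. Power alone would not justify a change. Eligibility, safety and complete safety reporting do, and the correction costs very little.

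**What to change.** 1. Reorder Section 10.3 so that the enrollment urine is collected, its opioid result read and the eligibility check completed before randomisation is assigned. This brings the list into line with Sections 2.1, 6.3 and 8.1.
2. In Section 15.1, remove the word *eligible* from the definition of the safety population, so that every randomised man who took drug is counted.
3. Reconcile Sections 6.3, 9.3.5.1 and 10.3 on two matters: whether an unconfirmed positive result excludes, and how dispensing relates to the result. Exclusion 4 does not mention confirmation, so making randomisation wait for the laboratory would in effect change the criterion. That choice is the sponsor's, and no clinical rule is proposed here.

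The urine is already collected at this visit, so no test is added. The cost is a change of wording and a slightly longer enrollment visit. With the result required first, q is zero and the stated 80% power is unaffected.
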